#### **Revised Text:**

Any medication taken within 7 days of study medication administration must be recorded in the CRF.

# Section 6.1.1. and 6.1.2.

2012N154431\_01 **CONFIDENTIAL** TRA117366

# **Section 7 Study Assessments and Procedures, Table 3**

**Description and reason for change:** Correction of study number within table as well as clarification of assessments.

Original Text:

Table 3 Time and Events Table

TRA115450	Screening 	Open-Label Treatment Period				Follow-up Period					
Study Day		Day 1	Weekly	Every 4 weeks	Every 6 weeks	End of Treatment 	1W FU 	2W FU 	3W FU 	4W FU	24W FU
Informed consent	Χ										
Medical history and evaluation of eligibility	Х										
Physical exam 		Χ									
Vital signs 		Χ	Χ	Χ	Χ	Χ	Χ	Χ	Χ	Χ	
Concurrent medication review		Х	Χ	Х	Х	Χ	Х	Χ	Χ	Χ	
Pregnancy test (urine) 		X 5	At leas	st every 8 w	/eeks					Χ	
CBC (incl. platelet count) 		Х	Χ	Х	Χ	Χ	Χ	Χ	Χ	Χ	
Peripheral blood smear 		Х	Χ	Х	Χ	Χ					
Clinical chemistry 		Х	Χ	Х	Χ	Χ	Χ	X 9	X 9	X 9	
Coagulation assays (INR/aPTT)		Х									
AE questioning		Х	Х	Χ	Х	Х	Χ	Χ	Χ	Χ	
Ophthalmic assessments 		Every 6 months X 						Χ			
Additional renal assessment 		If indicated 									

2012N154431\_01 **CONFIDENTIAL** TRA117366

### Table 3 Time and Events Table (Continued)

W: week; FU: follow-up; M: month

Note: If the subject continues on a stable dose of eltrombopag for 3 consecutive weeks, also if at the day 1 patient received stable dose in TRA115450 for at least 3 consecutive weeks (without changes in concomitant ITP therapy), assessments may be scheduled every 4 weeks ( $\pm 7$  days of nominal visit day) rather than weekly. If the subject continues on a stable dose of eltrombopag for 3 consecutive monthly visits (without changes in concomitant ITP therapy), including any consecutive monthly visits in TRA115450 prior to coming into this study, assessments frequency may be further reduced and may be scheduled every 6 weeks ( $\pm 7$  days of nominal visit day). If the dose of eltrombopag is not stable, weekly visits ( $\pm 3$  days of nominal visit day) will be required.

- 1. Screening visit may occur on the same day as the Day 1 visit.
- 2. All subjects will attend the End of Treatment visit on the day of or within 3 days after the last dose of study treatment.
- 3. Subjects who continue on treatment with eltrombopag (i.e., non-study treatment) will not be required to attend the Week 1, 2 and 3 Follow-up visits.
- 4. Physical Exam, including meadusrement and recording of the height and weight, to be performed at on Day 1. Vital signs to be performed at each visit and to include: heart rate and blood pressure.
- 5. For female subjects of child-bearing potential, a negative pregnancy test (urine or blood sample) MUST be obtained within 24 hours prior to the first dose. Tests to confirm that female subjects of childbearing potential are not pregnant will be conducted at least once every 8 weeks while receiving study treatment and after 4 weeks following completion or discontinuation of study treatment.
- 6. CBC parameters: to include platelet count, hemoglobin, hematocrit, RBC, WBC, WBC differential (absolute numbers). Reticulocytes will be measured if haemoglobin <10g/dl.
- 7. Peripheral blood smear to be performed on Day 1 and at least once every 6 weeks, regardless of the visit schedule (weekly or monthly).
- 8. Clinical Chemistry: Creatinine, alkaline phosphatase, AST, ALT, total bilirubin, direct bilirubin and albumin at each visit.
- 9. If clinical chemistry at follow-up week 1 is normal, no clinical chemistry will be measured at follow-up weeks 2, 3 and 4.
- 10. The last full ophthalmologic assessment conducted in the TRA115450 study will be used as the baseline ophthalmic assessment for this study. An age-appropriate full ophthalmologic assessment is required once standard of care exam will be performed to assess the presence of cataracts every 6 months while in the study treatment period, at the End of Treatment visit if not conducted within the prior 12 weeks, and at the 24 week follow-up visit.
- 11. The 'Additional renal assessments' will be done any time there is a creatinine increase considered clinically significant by the ininvestigator. Additional Renal assessments: urine dipstick, microscopic urinalysis, creatinine clearance, urine protein/creatinine ratio. If the urine protein/creatinine ration is > ULN, then a Urine Protein Electrophoresis should be performed,

#### **Revised Text:**

Refer to revised Time and Events table in Section 7, Table 3.

# **Section 7.2.1 Safety Endpoints**

**Description and reason for change:** Clarification of endpoints.

#### **Original Text:**

Safety and tolerability endpoints include blood pressure, heart rate, ocular examinations, clinical laboratory assessments and frequency of all adverse events, categorized using Common Terminology Criteria for Adverse Events (CTCAE) v4.03 toxicity grades.

#### **Revised Text:**

Safety and tolerability endpoints include clinical laboratory assessments and frequency of all adverse events, categorized using Common Terminology Criteria for Adverse Events (CTCAE) toxicity grades. Refer to the SPM for current version.

#### Section 7.2.1.1 General Considerations

**Description and reason for change:** Clarification to be consistent with revised assessments and match Time and Events Table.

#### **Original Text:**

Subjects will initially be evaluated on Day 1 with clinical assessments, vital signs, hematology, albumin, serum creatinine, platelet count and liver enzymes. Once the dose of eltrombopag and other ITP medications has been stable for 3 consecutive weeks, which may include the prior 3 weeks in the TRA115450 study, monthly visits will be acceptable unless in the investigator's opinion there is a specific medical reason for more frequent evaluations. If the dose is not stable, weekly visits will be required.

#### **Revised Text:**

Once the dose of eltrombopag and other ITP medications has been stable for 3 consecutive weeks, which may include the prior 3 weeks in the TRA115450 study, monthly visits will be acceptable unless in the investigator's opinion there is a specific medical reason for more frequent evaluations. If the dose is not stable, weekly visits will be required.

#### Section 7.2.1.2. Physical Exam

**Description and reason for change:** Clarification and the removal of vital signs.

#### **Original Text:**

#### Physical Exam

A physical examination will be done at Day 1 per the investigator's usual practice and any abnormal findings will be recorded on the appropriate form in the CRF, e.g, Medical History or AE/SAE form.

#### **Revised Text:**

#### Physical Exam

A physical examination will be done at the Day 1 per the investigator's usual practice, including measurement and recording of height and weight.

# Vital Signs

Vital sign measurements, done at each visit, will include systolic and diastolic blood pressure and heart rate. Vital sign measurements should be performed before any blood draws are performed.

#### **Section 7.2.1.4 Renal Monitoring**

**Description and reason for change:** Renal assessments have been removed.

#### **Deleted Text:**

Serum creatinine will be measured at each study visit and will serve as the main tool to check for global renal function.

'Additional renal assessments' will be performed at any time there is a creatinine increase deemed clinically significant by the investigator. No creatinine threshold value is prespecified, as the study will cover the whole pediatric age-range and creatinine values differ among the different age groups. When a subject requires the 'additional renal assessments', a visit should be scheduled within a week and the assessments repeated. The monitoring should be done weekly until abnormal renal values return to the normal range or baseline values.

'Additional renal assessments' will be assessed as follows:

- The urine protein/creatinine ratio (UP/CR) will be determined. If the UP/CR is above the upper limit of normal, then a urine protein electrophoresis (UPEP) will be performed.
- A microscopic urine analysis will be performed.
- A urine dipstick will be performed to look for pH, glucose, protein, blood and ketones. Urine dipstick will be performed locally using the dipsticks supplied by the central lab.

The glomerular filtration rate (GFR) will be estimated (creatinine clearance).

# **Section 7.5.1.5 Ophthalmic Assessments**

**Description and reason for change:** Title has been changed to reflect more streamlined assessment and focus on cataract assessment. Subsections 7.2.1.5.1. Baseline Ocular History and Risk Factors, 7.2.1.5.2 Ophthalmic Examinations and 7.2.1.5.4 Additional Ocular Follow-up have been removed.

#### **Original Text:**

Ophthalmic safety will be assessed in all subjects using the procedures listed below at the times listed in the Time and Events Table.

Ocular examinations will be performed by an ophthalmologist or an optometrist under the guidance of an ophthalmologist. Baseline and subsequent ocular assessments should be performed, whenever possible, by the same examiner.

#### **Revised Text:**

Ophthalmic safety, with focus on cataracts, will be assessed in all subjects following procedures used in standard practice at the times listed in the Time and Events Table.

Ocular examinations will be performed by an ophthalmologist or an optometrist under the guidance of an ophthalmologist. Assessments should be performed, whenever possible, by the same examiner.

Any abnormal findings will be recorded in the appropriate CRF form, e.g., Medical History or AE/SAE form.

#### **Section 7.2.4 Laboratory Assessments**

**Description and reason for change:** Laboratory assessments were streamlined. Table 4 has been amended to reflect this change.

#### **Original Text:**

All protocol required laboratory assessments listed in Table 4 will be performed by a local laboratory, in accordance with Table 3, Time and Events Table.

If any additional local laboratory assessments are undertaken during the course of the trial and they result in a change in patient management (for example SAE or AE or dose modification) the assessment data must be recorded in the patients CRF.

 Table 4
 Local Laboratory Assessments

Coagulation Assays	Chemistry
International normalized ration (INR)	Serum creatinine
Activated partial thromboplastin time (aPTT)	AST
	ALT
Peripheral Blood Smear	Total bilirubin
	Direct bilirubin
Hematology	Alkaline phosphatase
Platelet Count	Albumin
Red blood cell (RBC) count	
Reticulocytes if haemoglobin < 10g/dL	Urine Pregnancy 
Hemoglobin	
Hematocrit	Urinalysis, if indicated
WBC count (absolute count) with automated	Urine Dipstick:
differntial to include:	рН
Total neutrophils (absolute count)	Glucose
Lymphocytes (absolute count)	Protein
Monocytes (absolute count)	Blood
Eosinophils (absolute count)	Ketones
Basophils (absolute count)	Microscopic analysis
	Urine protein/creatinine ratio (UP/CR)
	Urine protein electrophoresis (UPEP), if indicated
	Glomerular filtration rate (GFR) (estimated using creatinine clrearance)

2. Refer to Section 7.2.3.1. For further details on pregnancy testing.

# **Revised Text:**

All protocol required laboratory assessments listed in Table 4 will be performed by a local laboratory, in accordance with Table 3, Time and Events Table, and recorded in the CRF, unless otherwise specified.

If any additional local laboratory assessments are undertaken during the course of the trial and they result in a change in patient management (for example SAE or AE or dose modification) the assessment data must be recorded in the patients CRF.

Table 4 Local Laboratory Assessments

	Chemistry	
	AST	
	ALT	
Peripheral Blood Smear	Total bilirubin	
	Direct bilirubin	
Hematology	Alkaline phosphatase	
Platelet Count		
	Urine Pregnancy 	
Hemoglobin		
WBC count (absolute count)		

3. Refer to Section 7.2.3.1. For further details on pregnancy testing. Results are not captured in CRF, but any pregnancy would be reported as specified in Section 7.2.3.

# Section 7.2.5. Meals and Dietary Restrictions

**Description and reason for change:** Clarification around administration of eltrombopag.

# **Original Text:**

Eltrombopag may be taken on an empty stomach (1 hour before or 2 hours after a meal) or with food containing little (<50 mg) or preferably no calcium or dairy products. (See Section 6.1, Permitted Medications and Non-Drug Therapies).

#### **Revised Text:**

Eltrombopag may be taken with food containing little (<50 mg) or preferably no calcium. (See Section 6.1, Permitted Medications and Non-Drug Therapies).

#### **Section 8 Data Management**

**Description and reason for change:** Clarification to data process and removal of repeated text.

#### **Original Text:**

For this study CRF Subject data will be collected using GSK defined case report forms and combined with data provided from other sources in a validated data.

Management of clinical data will be performed in accordance with applicable GSK standards and data cleaning procedures to ensure the integrity of the data, e.g., removing errors and inconsistencies in the data. Adverse events and concomitant medications terms will be coded using MedDRA and an internal validated medication dictionary, GSKDrug. In all cases, subject initials will not be collected or transmitted to GSK according to GSK policy.

Original CRFs will be retained by GSK, while the investigator will retain a copy.

#### **Revised Text:**

For this study subject data will be collected using GSK defined case report forms (CRFs) and data entered in a validated system.

Management of clinical data will be performed in accordance with applicable GSK standards and data cleaning procedures to ensure the integrity of the data, e.g., removing errors and inconsistencies in the data. Adverse events and concomitant medications terms will be coded using MedDRA and an internal validated medication dictionary, GSKDrug. In all cases, subject initials will not be collected or transmitted to GSK according to GSK policy.

Original CRFs will be retained by GSK, while the investigator will retain a copy.

#### Section 9.3.5. Key Elements of Analysis Plan

**Description and reason for change:** The Reporting and Analysis Plan has been removed. This section and each sub-section within have been changes for the modification of analysis and data collection. Changes for each section are highlighted below.

#### **Original Text:**

Data will be listed and summarized according to the GSK reporting standards, where applicable. Complete details will be documented in the RAP. And deviations from, or additions to, the original analysis plan described in this protocol will be documented in the RAP and final study report.

As it is anticipated that accrual will be spread thinly across centers and summaries of data by center would be unlikely to be informative, data from all participating centers will be pooled prior to analysis.

All data up to the time of study completion/withdrawal from study will be included in the analysis, regardless of duration of treatment.

As the duration of treatment for a given subject will depend on efficacy and tolerability, the duration of follow-up will vary between subjects. Consequently there will be no imputation for missing data.

Demographic and baseline characteristics will be summarized.

#### **Revised Text:**

Data will be displayed according to the GSK reporting standards, where applicable.

All data up to the time of study completion/withdrawal from study will be included in the displays, regardless of duration of treatment.

As the duration of treatment for a given subject will depend on efficacy and tolerability, the duration of follow-up will vary between subjects. Consequently there will be no imputation for missing data.

Demographic and baseline data will be displayed.

#### Section 9.3.5.1. Safety Analysis

# **Original Text:**

Safety analyses will be performed based on primary safety and tolerability endpoints that include blood pressure, heart rate, ocular examinations, clinical laboratory assessments and frequency of all adverse events, categorized using Common Terminology Criteria for Adverse Events (CTCAE) v4.03 toxicity grades.

The safety will be evaluated using descriptive statistics.

The SAFETY population defined as "All Treated Subjects" (ATS) population will be used for the analysis of safety data. Complete details of the safety analyses will be provided in the RAP.

#### **Revised Text:**

Safety displays will present safety and tolerability endpoints that include, clinical laboratory assessments and frequency of all adverse events, categorized using Common Terminology Criteria for Adverse Events (CTCAE) toxicity grades.

"All Treated Subjects" (ATS) population will be used for the presentation of safety data.

#### Section 9.3.5.1.1. Extent of Exposure

# **Original Text:**

The number of subjects administered study medication will be summarized according to the duration of therapy.

#### **Revised Test:**

Exposure data will be presented according to the duration of the subject's therapy.

#### 9.3.5.1.2. Adverse Events

# **Original Text:**

Adverse events (AEs) will be coded using the standard GlaxoSmithKline Medical Dictionary for Regulatory Activities (MedDRA) and grouped by system organ class. AEs will be graded by the investigator according to the –CTCAE (version 4.03).

Events will be summarized by frequency and proportion of total subjects, by system organ class and preferred term. Separate summaries will be fiven for all AEs, drugrelated AEs, serious AEs and AEs leading to discontinuation of study medication.

If the AE is listed in the NCI CTCAE(version 4.03) table, the maximum grade will be summarized.

The incidence of deaths and the primary cause of death will be summarized.

#### **Revised Text:**

Adverse events (AEs) will be coded using the standard GlaxoSmithKline Medical Dictionary for Regulatory Activities (MedDRA) and grouped by system organ class. AEs will be graded by the investigator according to the -CTCAE.

System organ class and preferred term of adverse events will be presented. Drug-related AEs, serious AEs and AEs leading to discontinuation of study medication will also be displayed.

If the AE is listed in the NCI CTCAE table, the maximum grade will be utilized where applicable.

The incidence of deaths and the primary cause of death will be presented.

## Section 9.3.5.1.3. Clinical Laboratory Evaluations

# **Original Text:**

Hematology and clinical chemistry data will be summarized at each scheduled assessment according to NCI CTCAE grade (version 4.03). The proportion of values lying outside the reference range will be presented for laboratory tests that are not graded because there are no associated NCI CTCAE criteria. Summaries will include date from scheduled assessments only, and all data will be reported according to the nominal visit date for which it was recorded (i.e. no visit windows will be applied). Unscheduled data will be included in "overall" and "any post-screening" summaries which will capture a worst case across all scheduled and unscheduled visits post first dose of study medication. Further details will be provided in the RAP.

#### **Revised Text:**

Hematology and clinical chemistry data will be displayed at each scheduled assessment according to NCI CTCAE grade. Unscheduled data will be included in "overall" and "any post-screening" displays which will capture a worst case across all scheduled and unscheduled visits post first dose of study medication.

#### Section 9.3.5.1.4. Other Safety Measures

#### **Original Text:**

The results of scheduled assessments of body weight, vital signs, will be summarized. Summaries will include data from scheduled assessments only. All data will be reported according to the nominal visit date for which it was recorded (i.e. no visit windows will be applied). All data will be listed. Further details will be provided in the RAP.

MedDRA	medical dictionary for drug regulatory affairs
PDS	programming data specifications
PT	preferred term
SAE	serious adverse event
SAP	statistical analysis plan
sd	standard deviation
SOC	system organ class

1 Introduction

This statistical analysis plan (SAP) provides detailed statistical methodology for the analyses of data which will be used for preparation of the ETB115BRU01 (TRA117366) clinical study report (CSR) and is based on the study protocol amendment 01, dated 08-Jul-2013.

The output shells information is in Section 7, the in-text table shells are in Section 8, the posttext tables and listings are in Section 9 and Section 10 respectively. Programming specifications for datasets, including derivation of variables, are given in the programming data specifications (PDS) document.

All data will be analyzed by and then imported to the Novartis global programming & statistical (GPS) environment. Analysis data sets and statistical outputs will be produced using the SAS system Version 9.3 or higher.

1.1 Study design

This is an open-label, phase III, extension study to evaluate the long-term safety of eltrombopag in pediatric patients with chronic immune (idiopathic) thrombocytopenic purpura (ITP) who previously participated in study TRA115450/PETIT2. This study will allow dosing of eltrombopag at an individualized dose for each patient based upon platelet count. The starting dose will be based on the patient's dose at the end of the TRA115450 study, unless a dose adjustment is warranted due to platelet count. The maximum dose will be 75 mg daily.

Maximum twelve (n = 12) patients will be enrolled into the study.

Patients may remain on treatment in this study until at least one of the following criteria is met: the patient reaches 18 years of age or eltrombopag receives local regulatory approval for the treatment of pediatric chronic ITP.

1.2 Study objectives and endpoints

Table 1-1Study objectives and endpoints

Objective	Endpoints
To provide continued treatment to patients who have completed the TRA115450/PETIT2 study and to describe the safety and tolerability of eltrombopag when administered to pediatric patients with previously treated chronic ITP.	Safety parameters include clinical laboratory assessments and frequency of all adverse events (AEs).
Primary objective The primary endpoint is the assessment of long-term safety.	Primary endpoint The frequency of all AEs.

2 Statistical methods

2.1 Data analysis general information

Categorical data will be presented as frequencies and percentages. For continuous data, n, mean, standard deviation, median, minimum, and maximum will be presented.

The analysis will be performed after database lock has occurred (after last patient last visit (LPLV)).

2.1.1 General definitions

Study day

The study day describes the day of the event related to the start date of eltrombopag.

The reference start date is designated as **Study Day 1.** Study Day –1 is the day that precedes Day 1. Study Day 0 is not defined. Study day is not to be used in numerical computations, for example in calculating exposure.

The study day will be calculated as:

- The date of the event (visit date, onset date of an event, assessment date etc.) reference start date + 1, if event is on or after the reference start date.
- The date of the event (visit date, onset date of an event, assessment date etc.) reference start date, if event precedes the reference start date.

The reference start date for all assessments (laboratory, ocular etc.) will be the start date of eltrombopag.

The study day will be displayed in the data listings. If an event starts before the reference start date, the study day displayed in the listing will be negative.

Pre-, on- and post-treatment periods

The overall observation period is divided into the following **mutually exclusive** periods:

- 1. Pre-treatment: prior to first dose of eltrombopag
- 2. **On-treatment**: from start date of eltrombopag to last date of study treatment + 30 days It is noted that if patient withdraws study informed consent or dies before then, then it is till the withdrawal/death date
- 3. **Post-treatment**: from last date of study treatment + 31 days to end of study

On-treatment assessments/events

The definition of on-treatment is given below, depending on the context.

For safety summary tables an on-treatment adverse event (AE) is defined as any AE reported in the following time interval (including the lower and upper limits):

• <date of first administration of study treatment; date of last administration of study treatment + 30 days>

Novartis	For business use only	Page 8
SAP and TFLs		CETB115BRU01/Eltrombopag

This corresponds to the definition of treatment-emergent AEs given in the protocol, i.e. AEs which are newly reported or worsening from baseline.

An on-treatment assessment is defined as any assessment performed after the date of first administration of study treatment (except for assessments specified to be collected post-dose on that day), i.e. assessments performed in the following time interval (including the lower and upper limits):

• <date of first administration of study treatment + 1; date of last administration of study treatment + 30 days>

For patients whose last date of study treatment is missing, on-treatment assessments/events include any assessment/event present in the database occurring after the start date of study treatment.

Listings will contain all data, flagging assessments/events outside of the on-treatment period where applicable.

Study treatment

Study treatment refers to eltrombopag.

Date of first administration of study treatment

The date of first administration of eltrombopag is derived as the first date when a nonzero dose eltrombopag is administered. This date is also referred to as *start date of study treatment*.

Date of last administration of study treatment

The date of last administration of eltrombopag is derived as the last date when a nonzero dose of eltrombopag is administered. This date is also referred to as *last date of study treatment*.

Duration of exposure

The duration of exposure is calculated as:

Duration of eltrombopag exposure (months) =[(last date of study treatment) - (first date of study treatment) + 1]/ 30.4375.

If the start or end date of eltrombopag is missing, the duration will be missing. The duration includes periods of temporary interruption (planned or actual) for any reason.

Definition of Months and Years

A month will be calculated as (365.25 / 12) = 30.4375 days. Where duration is to be reported in months, duration in days will be divided by 30.4375. Where duration is to be reported in years, duration in days will be divided by 365.25.

Time windows

Time windows for assessments are based on protocol specified windows.

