#### 7.2.2.5. Time Period and Frequency of Detecting AEs and SAEs

The investigator or site staff is responsible for detecting, documenting and reporting events that meet the definition of an AE or SAE.

AEs will be collected from the time the first dose of study treatment is administered until the 4-week follow-up visit.

SAEs will be collected over the same time period as stated above for AEs. In addition, any SAE assessed **as related** to study participation (e.g., protocol-mandated procedures, invasive tests, or change in existing therapy) or study treatment must be recorded from the time a subject consents to participate in the study up to and including the 4-week follow-up period. All SAEs will be reported to GSK within 24 hours, as indicated in Section 7.2.2.6.

After discontinuation of study treatment, the investigator will monitor all AEs/SAEs that are ongoing until resolution or stabilization of the event or until the subject is lost to follow-up. At any time after the 4-week follow-up visit the investigator may report any adverse event that they believe possibly related to study treatment.

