# 9.3.5. Key Elements of Analysis Plan

Data will be displayed according to the GSK reporting standards, where applicable.

All data up to the time of study completion/withdrawal from study will be included in the displays, regardless of duration of treatment.

As the duration of treatment for a given subject will depend on efficacy and tolerability, the duration of follow-up will vary between subjects. Consequently there will be no imputation for missing data.

Demographic and baseline data will be displayed.

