2.6.1 Adverse events (AEs)

The AEs will be re-coded using the latest version of the medical dictionary for regulatory activities (MedDRA) at the time of the analysis.

AEs will be graded using the common toxicity criteria for adverse events (CTCAE) Version 4.03. If a patient reported more than one AE with the same preferred term (PT), the AE with the greatest severity will be presented. If a patient reported more than one AE within the same primary system organ class (SOC), the patient will be counted only once with the greatest severity at the SOC level, where applicable. An AE with missing CTCAE grade will be included in the 'All grades' column of the summary tables.

In AE summaries, the primary SOC will be presented alphabetically and the PTs will be sorted within the primary SOC in descending frequency.

Summary tables will be provided for:

- All AEs regardless of relationship to study treatment by primary system organ class (SOC), preferred term (PT) and maximum severity
 - In-text table by SOC and maximum severity
 - In-text table by PT and maximum severity
- AEs suspected to be related to study treatment by SOC, PT and maximum severity
 - In-text table by PT and maximum severity
- AEs leading to treatment discontinuation regardless of relationship to study treatment by SOC, PT and maximum severity
 - In-text table by PT and maximum severity
- Serious AEs (SAEs) regardless of relationship to study treatment by SOC, PT and maximum severity
 - In-text table by PT and maximum severity
- On-treatment deaths by SOC and PT
 - In-text table by PT
- All deaths by SOC and PT
- *Non-SAEs regardless of relationship to study treatment (threshold=0%) by SOC and PT
- *On treatment deaths and SAEs by SOC and PT

*For the legal requirements of EudraCT, two required tables on <on-treatment/treatment emergent> AEs which are not SAEs with an incidence greater than x% and on <on-treatment/treatment emergent> SAEs and SAE suspected to be related to study treatment will be provided by SOC and PT on the ATS.

If for a same patient, several consecutive AEs (irrespective of study treatment causality, seriousness and severity) occurred with the same SOC and PT:

- a single occurrence will be counted if there is ≤ 1 day gap between the end date of the preceding AE and the start date of the consecutive AE
- more than one occurrence will be counted if there is > 1 day gap between the end date of the preceding AE and the start date of the consecutive AE

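### The SAP closes the AE summary window at last dose + 30 days, while the protocol collects to the actual 4-week visit and accepts later related reports, so a non-fatal event starting on day 31 or later appears only in a listing

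*SAP*

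**What the plan says.** SAP 2.1.1 sets the rule for AE tables: "For safety summary tables an on-treatment adverse event (AE) is defined as any AE reported in the following time interval", and the interval is "date of first administration of study treatment; date of last administration of study treatment + 30 days", both ends included. The post-treatment period then runs "from last date of study treatment + 31 days to end of study". The same section adds that this matches a definition of treatment-emergent AEs in the protocol. I find no such definition in the protocol text available.

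Protocol 7.2.2.5 has no 30-day limit. On AEs: "AEs will be collected from the time the first dose of study treatment is administered until the 4-week follow-up visit". On SAEs: "SAEs will be collected over the same time period as stated above for AEs". It then adds: "At any time after the 4-week follow-up visit the investigator may report any adverse event that they believe possibly related to study treatment".

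On what is displayed, Protocol 9.3.5 states: "All data up to the time of study completion/withdrawal from study will be included in the displays, regardless of duration of treatment". SAP 1.2 names the frequency of all AEs as the primary endpoint.

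SAP 2.6.1 provides an on-treatment deaths table and also "All deaths by SOC and PT". It has no such pair for SAEs or for AEs suspected to be related. All AEs are listed, with records outside the on-treatment period flagged. SAP Section 4 lists two changes from the protocol, the reporting standards and the clarified primary endpoint. The AE window is not among them.

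**The concern.** The protocol's collection period ends with a visit, and the SAP's summary window ends on a fixed day. When the visit comes later than that day, an event can be properly collected and still miss the tables that report the primary endpoint. Related events volunteered after the visit have no end date in the protocol, so a fixed cut-off in SAP 2.1.1 leaves out any that start after it.

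The study's purpose is long-term safety. Patients may stay on treatment until age 18 or local approval, the SAP plans exposure bands up to 60 months or more, and the analysis follows the last patient's last visit. A patient who stops early could therefore have a long interval before database lock in which a related event may be reported. Cataract is one possible example. Protocol 7.2.2.2 makes an ocular event of clinical concern a protocol-specific SAE, Table 3 schedules the eye examination only during treatment, and SAP 2.6.4.1 only lists ocular data. At stake is a related-AE or SAE table that shows none while the listing holds one.

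**Working it through.** **Inputs** (days are counted from the last dose)
- Upper limit of the AE summary window: day 30, inclusive (SAP 2.1.1).
- Start of the post-treatment period: day 31 (SAP 2.1.1).
- End of protocol collection: the actual 4-week visit, nominally 4 × 7 = day 28 (Protocol 3 and 7.2.2.5).
- Visit tolerance: ±3 days for weekly and ±7 days for monthly visits, both stated relative to Day 1 (Protocol 7). Applying either to a visit timed from the last dose is an assumption. Using ±7 further assumes that the single 4-week visit of patients who continue non-study eltrombopag counts as monthly.
- Study size: at most 12 (SAP 1.1).

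**Step 1: the plan's own figure.** Day 30 is a definition, not a calculated quantity. It agrees with the post-treatment period, since 30 + 1 = 31, so the two periods meet without a gap.

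**Step 2: when the visit can fall.**

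| Tolerance assumed | Possible visit days | Days past the limit |
|---|---|---|
| None | 28 | None (30 − 28 = 2 days to spare) |
| ±3 | 28 − 3 = 25 to 28 + 3 = 31 | 31 |
| ±7 | 28 − 7 = 21 to 28 + 7 = 35 | 31 to 35 |

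The mismatch within the collection period is therefore nil for a visit by day 30, one day under ±3, and five days under ±7.

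**Step 3: what *reported* means.** SAP 2.1.1 uses onset date as an event date when it defines study day, and SAP 6.1 imputes missing AE start dates. Both suggest that onset is meant. In that case an AE found at a day-31 visit that began by day 30 is still counted. If the date of reporting is meant, an AE that began on day 20 but was first reported on day 31 is left out. The text should say which.

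**Step 4: where an event starting on day 31 or later goes.**
- Fatal: it enters the all-deaths table.
- Non-fatal, last-dose date known: it goes to the flagged listing only.
- Non-fatal, last-dose date missing: it is counted, because SAP 2.1.1 then sets no upper limit. The same event is thus treated differently according to whether a date is complete.

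**Step 5: size per event.** SAP 2.6.1 counts a patient once per preferred term and once per system organ class. If 12 patients are treated and the affected patient has no other counted event in that category, the incidence changes by 1/12 = 8.3 percentage points. If the patient is already counted there, the change is 0.

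**The case against.** The case for leaving the SAP alone has real strength. Thirty days already exceeds the nominal 28-day follow-up. No sentence in SAP 2.6.1 expressly restricts every AE table to the on-treatment period, whereas SAP 2.6.3 does so for laboratory summaries. The table shells are not in the text available and might settle the matter. All AEs are listed and flagged, and with at most 12 patients a listing can be read in full. Reports after the 4-week visit are voluntary, and their handling is left to the Study Procedures Manual. Some patients will by then be taking non-study eltrombopag, so merging such events into study incidences would blur them.

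Most of this stands. It limits the size of the problem and rules out a single table with no time limit. It does not remove the mismatch. SAP 2.1.1 ties its definition to the safety summary tables, and SAP 2.6.1 describes the EudraCT tables as on-treatment or treatment-emergent, so the restrictive reading is the natural one. The SAP's own pair of deaths tables shows that an unrestricted companion table is practicable.

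A reader might also infer that the SAP breaches Protocol 9.3.5. The documents do not establish this. That commitment ends at study completion or withdrawal, and a listing can count as a display. For events volunteered after the 4-week visit it therefore gives little support.

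**Conclusion.** The point holds as a mismatch between collection and summary that should be corrected. Under the natural reading of SAP 2.1.1, a non-fatal AE or SAE with onset on day 31 or later is shown only in a listing, the SAP does not record this as a change, and the primary endpoint is worded as all AEs.

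The number of events affected is probably very small. The conclusion rests on three assumptions: the 2.1.1 definition governs the AE tables, which is implied rather than stated; the Protocol 7 tolerances, or an otherwise late visit, carry the 4-week visit past day 30; and later related reports reach the database before lock.

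Three stronger readings are not supported:
- That late events reach no summary table at all. Late deaths do, and so do events in patients without a last-dose date.
- That 1/7 = 14% (±3 days) or 5/15 = 33% (±7 days) of AEs would be lost. These are shares of possible visit dates, assumed equally likely, under a tolerance the protocol does not give for follow-up. They are not shares of AEs.
- That each omitted event shifts an incidence by at least 8.3 points. The shift is zero for a patient already counted in that category.

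**What to change.** 1. In SAP 2.1.1, set the upper limit of the AE summary window to the later of last dose + 30 days and the date of the actual 4-week follow-up visit. State that *reported* means onset. For AEs, start the post-treatment period on the following day so that the periods stay mutually exclusive, and check the end-date imputation in SAP Table 6-2 against the new limit.
2. In SAP 2.6.1, keep the on-treatment tables. As for deaths, add two supplementary tables by SOC and PT from the locked database: all SAEs, and all AEs suspected to be related. Show events after the 4-week visit separately and identify those in patients then taking non-study eltrombopag.
3. In SAP Section 4, record any restriction that remains. Correct or source the statement that the window matches a protocol definition of treatment-emergent AEs.

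The cost is some SAP wording and two small tables built from whatever the locked database holds. The drawback is that late events are volunteered rather than systematically collected. They should therefore stand beside the on-treatment incidence and not be merged into it.
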